## 8.5. Clinical Laboratory Parameters

If the reported value of a clinical laboratory parameter cannot be used in a statistical summary table due to, for example, that a character string is reported for a parameter of the numerical type, coded value needs to be appropriately determined and used in the statistical analyses ([Table 8](#)). However, the actual values as reported in the database will be presented in data listings.

Categorization of laboratory results into low/normal/high group will be done using the laboratory's scaled lower and upper limits of normal value as present in [Table 8](#) and [Table 9](#).

**Table 8: Example for Coding of Special Character Values for Clinical Laboratory Parameters**

Lab Test	Reported Lab Results (in SI units)	Coded Value for Analysis
Chemistry: ALT	<5	0

Lab Test	Reported Lab Results (in SI units)	Coded Value for Analysis
Chemistry: AST	<5	0
Chemistry: Bilirubin, Total	<2	0

**Table 9: Ranges of Potentially Clinically Significant Lab Values**

Parameter	SI Unit	Lower Limit	Higher Limit
CHEMISTRY			
Alanine			
Aminotransferase (ALT)	U/L		≥3 * UNL
Alkaline Phosphatase	U/L		≥3 * UNL
Aspartate Aminotransferase (AST)	U/L		≥3 * UNL
Bicarbonate	mmol/L		≥3 * UNL
Creatinine	mg/dL		>1.5 * Day 1
Potassium	mmol/L	<0.75*LLN	>1.2 * UNL
Sodium	mmol/L	<0.9*LLN	>1.1 * UNL
Chloride	mmol/L		
Total Bilirubin	mg/dL		>1.5 * UNL
Total Protein	g/dL	<0.9*LLN	>1.1 * UNL
Urea (BUN)	mg/dL		>1.5 * Day 1
HEMATOLOGY			
Red blood cell count (RBC)	10  /µL		
Hematocrit	%		
Hemoglobin	g/dL		
Mean corpuscular volume (MCV)	fL		
Mean corpuscular hemoglobin (MCH)	pg		
Mean corpuscular hemoglobin concentration (MCHC)	g/dL		
Neutrophil Percentage	%		

Parameter	SI Unit	Lower Limit	Higher Limit
Neutrophil Count	$10^3/\mu\text{L}$	$\leq 1$	
Lymphocyte Percentage	%		
Lymphocyte Count	$10^3/\mu\text{L}$		
Monocyte Percentage	%		
Monocyte Count	$10^3/\mu\text{L}$		
Eosinophil Percentage	%		
Eosinophil Count	$10^3/\mu\text{L}$		
Basophil Percentage	%		
Basophil Count	$10^3/\mu\text{L}$		
Platelet Count	$10^3/\mu\text{L}$	$\leq 100$	$\geq 700$
White Blood Cell Count	$10^3/\mu\text{L}$	$\leq 2.5$	$\geq 15$

LLN: Lower limit of normal, value provided by the laboratory

ULN: Upper limit of normal, value provided by the laboratory

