#### 4.4.3.2. Clinical Chemistry Tests

The clinical chemistry panel will be performed on blood obtained at Baseline, Week 8 Session 2 Light Session visit prior to the light session and during the End of Study follow-up visit. The panel will consist of the following tests:

- Serum sodium
- Serum potassium
- Serum chloride
- Serum bicarbonate (CO2)
- Alanine aminotransferase (ALT)
- Aspartate aminotransferase (AST)
- Total bilirubin
- Total protein
- Serum creatinine
- Blood urea nitrogen (BUN)
- Alkaline phosphatase

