## 7.2. Clinical Laboratory Parameters

Descriptive statistics for laboratory values (in US conventional and SI units) and changes from baseline at each assessment time point will be presented for the following laboratory parameters collected in the study including but are not limited to the following:

- Hematology: hemoglobin, hematocrit, RBC count, MCV, MCH, MCHC, WBC count, neutrophils, lymphocytes, monocytes, eosinophils, basophils, and platelet counts
- Chemistry: alkaline phosphatase, ALT, AST, bicarbonate, total bilirubin, BUN, chloride, creatinine, potassium, total protein, and sodium.

Laboratory tests values are clinically significant (CS) if they meet either the low or high CS defined by the normal ranges at the site's local laboratory. The number and percentage of subjects with post-Baseline CS values will be tabulated by treatment group. The percentages are to be calculated relative to the number of subjects with available non-CS baseline values and at least one post-Baseline assessment. The numerator is the total number of subjects with at least one post-Baseline CS value. In addition, shift tables will be presented by treatment group and time point. The following three data listings will be presented by subject:

- A listing of lab values for all lab tests at all collected time points.
- A listing of subjects with post-Baseline CS values will be provided including the Baseline and post-Baseline values.
- A listing of all AEs for subjects with CS laboratory values will also be provided.

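### SAP Table 9 gives bicarbonate the liver-enzyme limit and no lower limit, so low/normal/high categories built on that table cannot register any bicarbonate change

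*SAP*

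**What the plan says.** The bicarbonate row of SAP Table 9 reads "Bicarbonate mmol/L ≥3 * UNL". Its lower-limit cell is empty. The three rows directly above it (ALT, alkaline phosphatase, AST) have the same form, for example "Alkaline Phosphatase U/L ≥3 * UNL".

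The other electrolytes for which the table states limits are treated differently: "Potassium mmol/L <0.75*LLN >1.2 * UNL" and "Sodium mmol/L <0.9*LLN >1.1 * UNL". Chloride has no limits. The table's footnote says that the reference limits come from the laboratory ("Upper limit of normal, value provided by the laboratory"), so the SAP gives no value in mmol/L for bicarbonate. I read UNL in the table body and ULN in the footnote as the same quantity.

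Two sections bear on how these limits are used:

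- SAP 8.5: "Categorization of laboratory results into low/normal/high group will be done using the laboratory's scaled lower and upper limits of normal value". It points to Tables 8 and 9 for those limits. Table 8 holds only examples of how to code results reported with a less-than sign, so the scaled limits can come only from Table 9.
- SAP 7.2: laboratory values are clinically significant "if they meet either the low or high CS defined by the normal ranges at the site's local laboratory". This section names bicarbonate among the parameters and does not cite Table 9. It asks for descriptive statistics, counts of patients with clinically significant values, shift tables and a listing of all laboratory values.

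Bicarbonate is measured at Baseline, at the Week 8 Session 2 light visit and at End of Study (SAP 4.4.3.2). It belongs to the safety laboratory tests that form part of the secondary endpoint (SAP 4.2).

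**The concern.** A threefold upper limit suits an enzyme, which can rise many-fold. Bicarbonate is a tightly regulated electrolyte, and abnormal values in either direction lie close to the normal range. The row looks like a carry-over from the enzyme rows above it. That is an inference, but the SAP gives no reason for a one-sided threefold limit here.

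A row that states a criterion is also read differently from a blank row. A blank row visibly sets no criterion. This one appears to set one, so a table built on it would look like a negative screen for bicarbonate although the screen could not have returned a positive. Any shift table that takes its categories from Table 9 would have its bicarbonate result settled before the data are seen.

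**Working it through.** The plan states no absolute figure for bicarbonate, so there is none to reproduce. The check asks what each side of the row can flag, and then which outputs depend on it.

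**Low side.** The lower-limit cell is empty, so no low bicarbonate can be flagged under Table 9. This needs no assumption. The gap does not look like a fault in reading the table, because potassium, sodium and total protein show their lower limits in the same column.

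**High side.** The flag is 3 × ULN. The documents give no ULN, so I take a range of 26 to 32 mmol/L:

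| Assumed ULN (mmol/L) | Flag at 3 × ULN (mmol/L) |
|---|---|
| 26 | 78 |
| 28 | 84 |
| 30 | 90 |
| 32 | 96 |

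**Can such a value occur?** Use charge balance, chloride = sodium + potassium − bicarbonate − anion gap, with assumed sodium 135 to 145, potassium 3.5 to 5 and anion gap 4 to 16 mmol/L.

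- Bicarbonate 78: lowest implied chloride 135 + 3.5 − 78 − 16 = 44.5; highest 145 + 5 − 78 − 4 = 68 mmol/L.
- Bicarbonate 96: lowest 135 + 3.5 − 96 − 16 = 26.5; highest 145 + 5 − 96 − 4 = 50 mmol/L.

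With the other electrolytes in ordinary ranges, even the lowest flag in the assumed range requires a severely depleted chloride. The limit is out of practical reach across the whole range.

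**Scale against the table's own electrolyte factors.** Sodium and potassium use 1.1 and 1.2 × ULN, and 0.9 and 0.75 × LLN. Applied to bicarbonate with ULN 26 to 32 and an assumed LLN of 20 to 24 mmol/L:

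- Upper: 1.1 × 26 = 28.6 to 1.2 × 32 = 38.4 mmol/L.
- Lower: 0.75 × 20 = 15.0 to 0.9 × 24 = 21.6 mmol/L.

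These figures show only how far the present limit lies from the pattern used elsewhere in the table. They are not proposed limits.

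**Which outputs are affected.**

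- Under SAP 8.5 with Table 9, the low group is empty by definition and the high group is empty in practice. Every bicarbonate is grouped as normal at every visit, so a shift table on these groups cannot show a change.
- Under SAP 7.2, a bicarbonate outside the local laboratory's range, low or high, is counted as clinically significant. Table 9 plays no part.
- Section 7.2 asks for shift tables but does not say which categories they use, while 8.5 is the section that defines low/normal/high groups. The shift tables are therefore where the row is most likely to matter.

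**The case against.** The strongest case against the point is that the row may do little harm. Section 7.2 is the laboratory analysis section, and on its face it flags bicarbonate in both directions against local ranges. It also requires summary statistics, change from baseline and a listing of every value. Protocol 10.2 adds per-patient listings. With about 6 subjects, or up to 8 with replacements (Protocol 5.1 and 5.4), and three measurements each, there are about 6 × 3 = 18 to 8 × 3 = 24 bicarbonate values in all. An abnormal one would be seen without a flag. The study is descriptive, its primary objectives concern ECG and hypericin levels, and no decision depends on a bicarbonate category.

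All of that stands, and it limits the point to outputs driven by Table 9. A reader might infer from the row that the SAP will report every bicarbonate as not clinically significant whatever its value. The documents do not support that: the clinically significant counts and the listing of affected patients are defined in 7.2, without Table 9.

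It can also be said that an empty lower cell proves little by itself. Creatinine, total bilirubin and BUN are one-sided too, chloride has no limits, and most hematology rows are blank. That is fair: the table does not aim to flag every analyte in both directions. The stronger evidence is the upper limit, which uses an enzyme multiple for an electrolyte and so leaves the row with no working side.

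Finally, 8.5 is loosely written, since it cites Table 8 as a source of limits that Table 8 does not hold. That supports reconciling the two sections. It does not make the bicarbonate row workable.

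**Conclusion.** The bicarbonate row cannot do its job. The low side fails without any assumption. The high side fails at every assumed ULN from 26 to 32 mmol/L, where the flag needs 78 to 96 mmol/L. Low/normal/high categories for bicarbonate taken from Table 9 are fixed in advance, and so is any shift table built on them.

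Two stronger readings should be avoided. One is that no patient could ever reach the limit: the documents give no ULN, so the supportable statement is that the limit is not reachable in practice at any ordinary ULN. The other is that abnormal bicarbonate would go unreported across the SAP: section 7.2 uses local normal ranges and lists all values.

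Severity is minor. The row is wrong as a rule, but its reach depends on whether 8.5 with Table 9 or 7.2 drives the shift tables, and the SAP leaves that open.

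**What to change.** Before database lock:

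1. Replace the bicarbonate row of Table 9 with a two-sided limit in multiples of LLN and ULN near 1, in the form the table already uses for sodium and potassium. The sponsor's medical monitor should set the multiples.
2. Reconcile SAP 8.5 and Table 9 with SAP 7.2, so that one stated definition drives the clinically significant counts and the shift tables. Correct the reference to Table 8 in 8.5 at the same time.

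The cost is one table row and a clarifying sentence, and possibly a flagged value that would otherwise not appear. No data collection, visit or treatment changes.

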## 9. APPENDIX 2: SCHEDULE OF PROCEDURES

Subjects will be screened within 28 days of enrollment. Detailed timing of the assessments is shown in [Table 9](#).

**Table 10: Schedule of Assessments**

Time point	Blood Hypericin Concentration	ECG 	Light Session 	CAILS Evaluations	mSWAT	PGA	VAS itch	Skindex-29 QoL	Safety Assessments 	AE Collection
Screening 										
Baseline 	X 	X 		X 	X 		X 	X 	X 	
Week 1, Session 1			X				X			X
Week 1, Session 2			X				X			X
Week 2, Session 1			X				X			X
Week 2, Session 2			X				X			X
Week 3, Session 1			X				X			X
Week 3, Session 2			X				X			X
Week 4, Session 1			X				X			X
Week 4, Session 2	X  X 	X  X 	X				X			X
Week 5, Session 1			X				X			X
Week 5, Session 2			X				X			X
Week 6, Session 1			X				X			X
Week 6, Session 2	X 	X 	X				X			X

Time point	Blood Hypericin Concentration	ECG 	Light Session 	CAILS Evaluations	mSWAT	PGA	VAS itch	Skindex-29 QoL	Safety Assessments 	AE Collection
Week 7, Session 1			X				X			X
Week 7, Session 2			X				X			X
Week 8, Session 1			X				X			X
Week 8, Session 2 Drug Application	X 									X
Week 8, Session 2 Light Session	X  X 	X  X 	X				X	X	X 	X
Week 10/End of Study	X	X		X	X	X	X		X	X

 ECG will include a standard 12-lead reading with QT interval measurements. Correction for heart rate will be performed electronically using both the Bazett's and Fridericia formulas.

 Light Session: Includes application of drug 18-24 hours earlier by the patient and the Erythema Scoring performed 5-10 minutes before and after light therapy

 Safety Assessments: consists of vital signs, and hematology and clinical chemistry blood tests

 The following assessments will be performed at the Screening visit: Obtain Informed Consent Form (ICF) signature, Assessment of entry criteria, Complete Medical History, Complete Vital Signs, Serum HCG pregnancy test (women of childbearing age only)

 Baseline: Includes interval medical history from screening, Complete Physical Examination, review of the results of the serum pregnancy test for eligible female subjects, and charting of index lesions onto the Body Lesion Diagram.

 Obtained prior to drug application

 Prior to light session

 2 hours after completion of the light session
